9.7.2 Lost to Follow-Up

The study only has one visit with two voids. There are no follow-up visits.

10.0 PROCEDURES

Adherence to the study design requirements, including those specified in the CIP, is essential and required for study conduct.

All screening evaluations must be completed and reviewed to confirm that potential participants meet all eligibility criteria. The investigator will maintain a screening log to record details of all participants screened and to confirm eligibility or record reasons for screening failure, as applicable.

10.1 Screening and Enrollment Procedures

All participants will be screened against the inclusion and exclusion criteria (see section 9.1 & 9.2). Participants who fail to meet eligibility criteria must not have a study device placed.

The Investigator or their designee will explain the study to the participant, answer all of the participant's questions, and obtain written informed consent (and assent, as applicable) before the collection of any study data or performance of any study procedures.

 BD	Document Type: Global Clinical	Page No: 16 of 59
	Title: Clinical Investigation Plan Study ID: UCC-23AC023	Version No: 1.0

Template GFM-10095B

10.2 Medical History / Baseline Assessments

Participants demographic information including age, race, ethnicity, sex, height, and weight (for BMI calculation) will be collected at baseline.

10.3 Randomization

The site will receive a randomization list of placement sequence numbers. Participants can only be randomized when all eligibility criteria are met, and consent has been obtained.

10.4 Evaluation Procedures

Once participants meet all the inclusion, none of the exclusion criteria and are randomized, participants will go through the activities below.

Steps	Activity 1 (Prior to placing the device)
1.1	
After enrollment and completion of baseline data collection, the participant will be escorted to a test room. Participant will be asked to remove all clothing and change into a gown. The participants may leave on a shirt if desired.
 
 Female participants may keep on a bra if desired Male participants – Unless the participant arrives to the clinical site with their pubic hair pre-trimmed, the participant's pubic hair will be clipped by themselves (or guardian/parent) or the HCP.
1.2	
Prior to the participant's arrival to the test room, the bed will be prepared with clean sheets. A pre-weighed absorbent pad will be placed in the middle of the bed. A pre-weighed canister (weighed with lid) will be will be available for the participant to connect.

Note to site	Make sure top of mattress and PUCS height remains the same for all participants in the study.
1.3	
The participant will be trained on device use per the Instructions for Use and a training video. The participant will be allowed to refer to any of the training materials that are available and provided to them throughout the study procedures.

1.4	
The HCP will set-up the PUCS per the IFU. The HCP will confirm proper assembly by performing the following:
 
 check that the PUCS lid is securely snapped. check that all tubing and elbow connections on the lid are secure. confirm power connections are secure. ensure the Green LED light on the power switch is on. 
The HCP will adjust the PUCS as needed prior to continuing to next steps.

1.5	
The participant will be asked to lie on their back on the bed and to leave their hands resting on their stomach, when possible, while they are lying on their back. For participant comfort, the head of the bed will be slightly elevated.

1.6	
The participant (or guardian/parent) or HCP will clean the participant's anatomy with the provided wipes. The HCP will confirm the participant cleaned their anatomy.

 BD	Document Type: Global Clinical	Page No: 17 of 59
	Title: Clinical Investigation Plan Study ID: UCC-23AC023	Version No: 1.0

Template GFM-10095B

1.7	
The HCP will perform a skin integrity check and note any existing signs or symptoms of irritation in the perineal area. If the participant's skin is compromised, the HCP will consult the site staff before proceeding with placement of study device and/or withdraw the participant.
 
HCP will confirm if no signs or symptoms of irritation in the perineal area was noted.

Steps	Activity 2 (Placement of device)
2.1	The participant will be given either the PureWick™ Male External Catheter (male participants only) or PureWick™ Flex Female External Catheter (female participants only).
2.2	For female participants only: The participant (or guardian/parent) or HCP will curve the PW Flex to fit the participant's anatomy per the IFU.
2.3	
The PW MEC or PW Flex will be connected to the canister via collector tubing per the IFU. Tubing connection to be done by the participant (or guardian/parent) for the self-placed void and by the HCP for the HCP-placed void. The HCP will confirm and record if the tubing connection was made correctly for the self-placed void. If the connection was not done correctly, the HCP will capture the reason:
 
 1. The participant did not understand how to make the connection 2. The participant connected the device to the wrong tubing port 3. The participant was not physically able to make the connection with sufficient force 4. Other, specify 
The HCP will adjust tubing connection prior to void if it was not done correctly.

2.4	Based off the randomization of placement sequence, the participant will self-place (or guardian/parent) the device or the HCP will place the device.
2.5	
If device was self-placed (or guardian/parent), the HCP will confirm the placement of the PureWick™ Male External Catheter (male participants only) or PureWick™ Flex Female External Catheter (female participants only). If the device is not placed correctly, the HCP will ask the participant to reposition/adjust the device. The HCP will record if any adjustments were made.
 
Even when placed correctly, participants may adjust the device as needed for comfort. The HCP will record if any adjustments were made.

Steps	Activity 3 (Void #1)
3.1	The HCP will confirm that the absorbent bed pad is appropriately positioned under the participant.
3.2	The participant will be asked to void in the supine position. The participant will be instructed not to strain or attempt to regulate their urine flow.
Steps	Activity 4 (Removing the device)
4.1	
After the completion of the void the participant (or guardian/parent) or HCP (based off placement sequence) will carefully remove the device per the instructions for use.
 
 • For female participants, HCP will record if the device has dislodged after the void prior to device removal
4.2	The HCP will record whether they observed any urine leak from the device upon removal.

	Document Type: Global Clinical Title: Clinical Investigation Plan Study ID: UCC-23AC023	Page No: 18 of 59
		Version No: 1.0

Template GFM-10095B

4.3	The HCP will lift the catheter and tubing to make sure all the liquid flows into the canister.
4.4	The HCP will perform a skin integrity check and note any signs of irritation in the perineal area or adverse reactions. HCP will confirm if no signs or symptoms of irritation in the perineal area were noted.
4.5	The HCP will turn the PUCS suction OFF by flipping the black switch on the PUCS.
4.6	The used absorbent pad will be weighed by the HCP, and the value documented on the appropriate CRF. The canister (with lid) with urine will be weighed by the HCP and documented. The used catheter will be disconnected from the tubing and discarded.
4.7	The participant will be asked to complete all applicable questionnaires.
Steps	Activity 5 (Void #2)
5.1	After completion of void 1, the participant will be instructed to drink fluids in preparation for void 2.
5.2	Approximately 30 minutes after void 1 or when the participant feels the need to void again, the participant will proceed with void 2 (the participant will not use the same wetted device but a new clean device). Steps in Activities 1-4 will be repeated for the 2 nd void based off the placement sequence.
Steps	Activity 6 (After Completion of Both Voids)
6.1	Once the participant has completed both voids, the participant will be asked to complete the remaining required questionnaire.
6.2	Each HCP will complete the ease-of-use questionnaire after completing all study activities.

Questionnaires to be completed

Person to complete questionnaire	Questionnaire to complete	When to complete
Participant	Perception of wetness	After each void
Participant	Ease of use	After self-placement void
Participant	Comfort	After completion of all voids
Participant	IFU Evaluation	After self-placement void
HCP	Ease of use	After completion of all participants. Each HCP completes this questionnaire once per device.

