3. Trim or clip the pubic hair to ensure the product securely adheres to the skin. Check the skin and do not use if there is irritation or breakdown. Clean the penis and the skin around the base of the penis with soap and water or soap and water wipes. Dry skin prior to positioning the device.
NOTE: Moisture or soap residue on skin will weaken the adhesive.
4. Position the device, aligning drainage fitting towards the feet of the user. Slide the opening of the device over the penis until close to, but not touching, the skin around the base of the penis. Center penis within the opening. Do not place scrotum inside the device. Remove the bottom adhesive peel-off and press the device against the skin below the base of the penis. Remove the top adhesive peel-off and press the device against the skin above the base of the penis. Ensure device has fully adhered around the base of the penis by pressing down on the adhesive.

Removal of PureWick™ Male External Catheter

5. Gently lift the top edge of the adhesive base off the skin. In a slow, downward peeling motion, remove the device. If necessary, use a warm, wet cloth or pad to help loosen adhesive.
Warning: To avoid potential skin injury, never pull the device directly away from the user. Always peel in the direction from head to foot.
- After use, this product may be a potential biohazard. Dispose of in accordance with applicable local, state, and federal laws and regulations.

When to Replace PureWick™ Male External Catheter

6. Replace the device at least every 24 hours or if soiled with feces, blood, or semen.

Wall Suction

This product is compatible with wall suction in hospital-like settings. If using this set-up, connect the canister to wall suction and set to a minimum of 40 mmHg continuous suction. Always use the minimum amount of suction necessary.

BD, the BD Logo and PureWick are trademarks of Becton, Dickinson and Company, or its affiliate.
 © 2023 BD and its subsidiaries. All rights reserved.

 Manufacturer:
 C. R. Bard, Inc.
 [name]
 [name]
 [name]
 bd.com

	Document Type: Global Clinical	Page No: 35 of 59
	Title: Clinical Investigation Plan Study ID: UCC-23AC023	Version No: 1.0

Template GFM-10095B

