2.2.2 Primary Endpoint 1 - Capture Rate

Weight of Captured Urine = *Canister final weight – Canister starting weight*

Weight of Urine Leak = *Bed pad final weight – Bed pad starting weight*

Void Weight = *Weight of Captured Urine + Weight of Urine Leak*

Capture Rate =
$$\frac{\text{weight of captured urine} \times 100\%}{\text{weight of captured urine} + \text{weight of urine leak}}$$

Voids with weight (captured + leak) ≥ 10 g is considered evaluable.

Capture rate is calculated from evaluable voids only.

Table 8a Void Summary by Device

ITT

	PureWick Flex Female (N = xx)	PureWick Male (N = xx)
Captured Weight (g)		
N	xxx	xxx
Mean (SD)	xx.x (xx.x)	xx.x (xx.x)
Median	xx.x	xx.x
Min – Max	xxx-xxx	xxx-xxx
Leaked Weight (g)		
N	xxx	xxx
Mean (SD)	xx.x (xx.x)	xx.x (xx.x)
Median	xx.x	xx.x
Min – Max	xxx-xxx	xxx-xxx
Void Weight (g)		
N	xxx	xxx
Mean (SD)	xx.x (xx.x)	xx.x (xx.x)
Median	xx.x	xx.x
Min – Max	xxx-xxx	xxx-xxx
Evaluable Void	n (%)	n (%)

Table 8b Capture Rate by Device

ITT

Capture Rate (Evaluable Voids Only)	PureWick Flex Female Evaluable (N ₁ = xx)	PureWick Male Evaluable (N ₁ = xx)
Mean (SD)	xx.x% (xx.x%)	xx.x% (xx.x%)
Median	xx.x%	xx.x%
Min - Max	xx.x%	xx.x%

THIS SUBJECT MATTER IS RESTRICTED SOLELY FOR THE USE OF BECTON DICKINSON AND COMPANY AND ITS SUBSIDIARIES

	Title: UCC-23AC023 Statistical Analysis Plan Table shells	Page No. 17 of 33
	Study Title: UCC-23AC023 PureWick Adolescent Study CIP/CPSP Version: 1.0	Version No: 1.0

Template GFM-10082B

Note: Voids with weight (captured + leak) ≥ 10 g is considered evaluable.**Table 9a Void Summary by Device and Placement**

ITT

	HCP			SelfPlaced		
Device	PureWick Flex Female (N = xx)	PureWick Male (N = xx)	HCP Overall (N = xx)	PureWick Flex Female (N = xx)	PureWick Male (N = xx)	SelfPlaced Overall (N = xx)
Captured Weight (g)						
N	xxx	xxx	xxx	xxx	xxx	xxx
Mean (SD)	xx.x (xx.x)	xx.x (xx.x)	xx.x (xx.x)	xx.x (xx.x)	xx.x (xx.x)	xx.x (xx.x)
Median	xx.x	xx.x	xx.x	xx.x	xx.x	xx.x
Min – Max	XXX-XXX	XXX-XXX	XXX-XXX	XXX-XXX	XXX-XXX	XXX-XXX
Leaked Weight (g)						
N	xxx	xxx	xxx	xxx	xxx	xxx
Mean (SD)	xx.x (xx.x)	xx.x (xx.x)	xx.x (xx.x)	xx.x (xx.x)	xx.x (xx.x)	xx.x (xx.x)
Median	xx.x	xx.x	xx.x	xx.x	xx.x	xx.x
Min – Max	XXX-XXX	XXX-XXX	XXX-XXX	XXX-XXX	XXX-XXX	XXX-XXX
Void Weight (g)						
N	xxx	xxx	xxx	xxx	xxx	xxx
Mean (SD)	xx.x (xx.x)	xx.x (xx.x)	xx.x (xx.x)	xx.x (xx.x)	xx.x (xx.x)	xx.x (xx.x)
Median	xx.x	xx.x	xx.x	xx.x	xx.x	xx.x
Min – Max	XXX-XXX	XXX-XXX	XXX-XXX	XXX-XXX	XXX-XXX	XXX-XXX

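### The leak pad is weighed and on the bed before the participant is cleaned with wipes, so any wipe fluid that reaches it counts as leaked urine

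*Protocol*

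**What the plan says.** Protocol section 10.4 sets the order of events at each void.

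- Step 1.2, before the participant reaches the test room: "A pre-weighed absorbent pad will be placed in the middle of the bed".
- Step 1.5: "The participant will be asked to lie on their back on the bed".
- Step 1.6: "The participant (or guardian/parent) or HCP will clean the participant's anatomy with the provided wipes". The HCP confirms that cleaning was done. Drying is not mentioned.
- Step 3.1, after the device is placed: "The HCP will confirm that the absorbent bed pad is appropriately positioned under the participant". This checks position only.
- Step 4.6, after the void and device removal: "The used absorbent pad will be weighed by the HCP, and the value documented on the appropriate CRF".
- Step 5.2 repeats Activities 1 to 4, so void 2 follows the same order.

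SAP section 2.2.2 defines the weight of urine leak as "Bed pad final weight – Bed pad starting weight". Capture rate is captured weight divided by captured plus leaked weight, and a void is evaluable when that sum is at least 10 g.

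The male catheter IFU (protocol Appendix 1) tells the user to dry the skin after cleaning and gives the reason: "NOTE: Moisture or soap residue on skin will weaken the adhesive". The female catheter IFU (Appendix 2) asks for cleaning and has no drying line.

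**The concern.** The starting weight of the pad is fixed before a wet procedure carried out on the bed where the pad lies, and the final weight is taken after the void. Nothing in between separates wipe fluid from urine: the pad is not re-weighed or changed, and no blank is subtracted. Whatever fluid the pad picks up during cleaning is therefore analysed as device leakage.

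The plan has no performance goal (protocol section 6.2) and no formal test (section 11.0), so the descriptive capture rate is itself the evidence offered for the wider indication (section 7.2). An avoidable error that always pushes that figure the same way is worth removing. Fluid on the pad can also carry a void below 10 g over the evaluability limit, where it would be analysed with a distorted rate instead of being set aside.

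**Working it through.** The plan states no figure that can be reproduced here, so the check applies the SAP formula to an assumed amount of wipe fluid.

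**Inputs**
- Capture rate and leak definition: SAP section 2.2.2.
- Evaluability limit, captured plus leak of at least 10 g: SAP section 2.2.2.
- m, wipe fluid on the pad: not in the documents. Assumed range 0 to 5 g, with zero included.
- V, true void weight: not in the documents beyond the 10 g limit. Values of 10, 100 and 300 g are used as illustrations.

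**Formula.** Measured leak is true leak plus m. With true capture of 100%, V is all captured and the measured rate is V/(V + m). With true capture of 90%, it is 0.9V/(V + m). Leak appears only in the denominator, so the bias is downward for any m above zero.

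**Measured capture, true capture 100%**

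| V (g) | m = 0 | m = 1 g | m = 5 g |
|---|---|---|---|
| 300 | 100% | 300/301 = 99.7% | 300/305 = 98.4% |
| 100 | 100% | 100/101 = 99.0% | 100/105 = 95.2% |
| 10 | 100% | 10/11 = 90.9% | 10/15 = 66.7% |

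**Measured capture, true capture 90%, m = 5 g.** 300 g: 270/305 = 88.5%. 100 g: 90/105 = 85.7%. 10 g: 9/15 = 60.0%.

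**When the error is negligible.** With no true leak, the loss stays below one percentage point when m/(V + m) < 0.01, that is, when V > 99m. This means more than 99 g for 1 g of fluid and more than 495 g for 5 g.

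**Evaluability.** The fluid counts towards the 10 g. A true void of 9 g, fully captured, with 1 g of fluid becomes evaluable and reads 9/10 = 90.0%. With 5 g of fluid, a true void of 5 g would qualify and read 5/10 = 50.0%.

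**The case against.** **The participant may not be on the pad during cleaning.** Step 1.2 puts the pad mid-bed and step 1.5 puts the participant on the bed. Only step 3.1, after cleaning, says the pad is underneath. Contact during step 1.6 is thus an inference. It is the natural reading, since no step introduces the pad later, but the text does not state it.

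**The amount is unknown and may be nil.** This stands. The lowest figure in the table needs both 5 g of fluid and a 10 g void, and protocol section 8.2.2 has participants drink between voids to secure a full second void. Against that, void 2 may follow after about 30 minutes (step 5.2), and any void from 10 g is analysed.

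**The bias cannot flatter the capture rate, and no decision rule depends on it.** This also stands and limits the weight of the point. A primary endpoint should still measure urine only.

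**The protocol does not contradict the male IFU.** Correct: step 1.6 omits drying but does not forbid it. Step 1.3 trains participants on the IFU and leaves it available to them, which covers the gap in part. Drying the skin would not, however, take back fluid already on the pad.

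**Stronger readings that the documents do not support**
- A reader might infer that damp skin lowers the wetness score. The item in Appendix 4 asks how the participant felt after urinating, and nothing in the documents allows such an effect to be shown or sized.
- A reader might infer a bias between HCP-placed and self-placed voids. Step 1.6 does not tie who cleans to the placement sequence, unlike steps 2.4 and 4.1, so no systematic difference follows.
- A reader might want a dryness check for both devices. The female IFU has no drying instruction, so this would add a device-use rule that is not in that label.

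**Conclusion.** The point holds as a limited measurement flaw. As written, the order of steps lets wipe fluid enter the pad weight, and the SAP has no means of taking it out. Any such fluid lowers the capture rate and adds to the 10 g evaluability total.

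On the assumption of 0 to 5 g and true capture of 100%, the loss is 0 to 1.6 percentage points at 300 g, 0 to 4.8 at 100 g and 0 to 33.3 at 10 g. It is minor for full voids and material only for small ones. The conclusion rests on two things the documents do not settle: that the participant is over the pad while being cleaned, and that some fluid reaches it.

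The silence of step 1.6 on drying, set against the male IFU, is a separate gap to be reconciled. It is an omission and not an opposite instruction. The documents do not show that it would cause adhesive failure in this study.

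**What to change.** In section 10.4, make one of these changes for both voids:

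- Clean the participant on a separate underpad, remove it, and place the pre-weighed pad after step 1.6. The position check in step 3.1 can stay as it is.
- Or keep the present order, re-weigh the pad after cleaning, and record that value as the starting weight used in SAP section 2.2.2.

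Either change keeps out of the leak weight whatever reached the bed up to that point. Some transfer from damp skin afterwards remains possible, so the pad is best placed or re-weighed as late as practical before the void. The cost is one spare disposable pad or one extra weighing per void, with no new visit and no change to the formula.

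Separately, the sponsor should reconcile step 1.6 with the drying instruction in the male IFU, so that the protocol and Appendix 1 describe the same preparation.

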4.2 Rationale

The purpose of this study is to understand if external catheters are an effective alternative in the adolescent population in both male and female adolescents in the setting where the external catheter is placed by a healthcare professional as well as in the outpatient or home setting where the external catheter is self-placed or placed by guardian/parent, and to provide data to support potential labeling for an expanded population use. Specifically, the study will collect data about how the external catheters perform in terms of capture rate when participants are voiding after self-placement of the device, if the adolescent participant can use the device independently or with the help of a guardian/parent and collect any adverse events that are reported.

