**Figure 3**

6.0 OBJECTIVES AND HYPOTHESES

6.1 Objectives and Endpoints

Objective Type	Objective	Endpoint
Primary	
 To assess the performance of the PureWick™ Flex FEC and PureWick™ MEC in adolescents after HCP placement and participant (or guardian/parent) placement 	
 Capture rate following void (captured as % of urine captured by device and collected in canister measured by weight) Perception of wetness following each void on a 5-point Likert scale (brief questionnaire)
Secondary	
 To assess ease of use by HCP and participant To assess participant comfort after using the PureWick™ FEC or PureWick™ MEC 	
 Ease of use score on a 5-point Likert scale (brief questionnaire) Overall comfort score on a 5-point Likert scale (brief questionnaire)

	Document Type: Global Clinical	Page No: 9 of 59
	Title: Clinical Investigation Plan Study ID: UCC-23AC023	Version No: 1.0

Template GFM-10095B

	
 To evaluate the Instructions for Use in the adolescent population 	
 IFU comprehension score on a 5-point Likert scale (brief questionnaire)
--	---	---

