7.0 DESIGN OF THE STUDY

7.1 Overall Design

This prospective, uncontrolled, open-label, single-center, healthy volunteer study will assess the performance of the PureWick™ System in adolescents following a void with HCP placement of the device and a void with participant (or guardian/parent) placement of the device. Male participants will evaluate the PureWick™ Male External Catheter and female participants will evaluate the PureWick™ Flex Female External Catheter.

The expected participation time is approximately 2-3 hours, divided across two voids. Prior to the first void, each participant will be consented and trained on device instructions for use.

For each device evaluation, participants will have the device placed by a healthcare professional (HCP) for one void and will self-place the device for the other void. The participant may have a guardian or parent place the device only if the participant is unable or unwilling to self-place the device. With the device in place, participants will urinate two separate times during the study to evaluate the performance of the device in the adolescent population. After each void, the device will be removed by the HCP or self-removed (a guardian or parent may remove the device if the participant is unable or unwilling to remove the device). Finally, the participants will be asked to complete brief questionnaires to assess perceived wetness, IFU comprehension, comfort and ease of use. HCPs will also be asked to complete questions about ease of use for the voids in which they placed and removed the device.

Approximately 40 healthy participants (20 male and 20 female) will be enrolled into the study. The study will be conducted at one clinical site.

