26.3 Appendix 3 - PureWick™ Urine Collection System

**Welcome**

Thank you for purchasing the PureWick™ Urine Collection System, the system to be used with PureWick™ External Catheters. The device pulls urine through tubing that is connected to a collection canister. Urine is stored in the collection canister for proper disposal. This product may be used in both home environments and professional care facilities.

Please read all operating instructions and warnings before the first use of this product. No special skills or additional training is required.

Intended Users

The PureWick™ Urine Collection System is intended to be operated by:

- User/Patient
- Caregiver/Healthcare professional

All functions can be safely performed by the individuals above.

Indications for Use

The PureWick™ Urine Collection System is to be used with PureWick™ External Catheters which are intended for non-invasive urine output management.

Contraindications for Use

Do not use the PureWick™ Urine Collection System with PureWick™ External Catheters on individuals with urinary retention.

Safety and Warnings

Always unplug PureWick™ Urine Collection System before cleaning or when not in use.

DO NOT IMMERSE THE PUREWICK™ URINE COLLECTION SYSTEM IN WATER. As with most electrical devices, electrical parts in this system are electrically live even when the power is off. To reduce the risk of electric shock, if the PureWick™ Urine Collection System falls into water, unplug immediately. DO NOT REACH INTO THE WATER TO RETRIEVE IT.

WARNING: Contains small parts that may cause choking. Keep out of reach of children.

Keep cords and tubing out of the reach of children to avoid the risk of strangulation.

Discontinue use if an allergic reaction occurs. Not recommended for users who are experiencing skin irritation or skin breakdown in device contact areas.

WARNING: This device should not be used in oxygen rich environments or in conjunction with flammable anesthetics.

	Document Type: Global Clinical	Page No: 38 of 59
	Title: Clinical Investigation Plan Study ID: UCC-23AC023	Version No: 1.0

Template GFM-10095B

If the PureWick™ Urine Collection System is dropped or tipped over spilling urine, unplug the unit and carefully inspect for loose or damaged parts before resuming use. Contact Customer Support at [name] if any damage is observed.

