26.7 Appendix 7 – Participant IFU Evaluation Questionnaire (Both Male and Female)

Participant Number:	Device:					
	 PureWick Male External Catheter					
	 PureWick Flex Female External Catheter					
After Self-Placement Void						
Please respond to the following questions regarding the PureWick™ External Catheter on a scale of 1-5, where 1 is Strongly Disagree, and 5 is Strongly Agree.						
		Strongly Disagree	Disagree	Neutral	Agree	Strongly Agree
	Questions	1	2	3	4	5
1	I was able to understand and follow the written instructions in the PureWick™ External Catheter instructions for use so that I could perform the steps myself.					
1a	If you selected 1, 2 or 3, please provide comments to tell us why you answered as you did (free text).					
2	I was able to understand the pictures in the PureWick™ External Catheter instructions for use so that I could perform the steps myself.					
2a	If you selected 1, 2 or 3, please provide comments to tell us why you answered as you did (free text).					
3	I was able to place the PureWick™ external catheter on myself.					
3a	If you selected 1, 2 or 3, please provide comments to tell us why you answered as you did (free text).					

	Document Type: Global Clinical Title: Clinical Investigation Plan Study ID: UCC-23AC023	Page No: 59 of 59
		Version No: 1.0

Template GFM-10095B

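### The IFU comprehension score is collected only after training and a video, so it cannot show whether adolescents understand the IFU itself

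*Protocol*

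**What the plan says.** Protocol Section 6.1 lists among the secondary objectives "To evaluate the Instructions for Use in the adolescent population", with a comprehension score on a 5-point scale as the endpoint. The score comes from Appendix 7, whose first item reads, in part, "I was able to understand and follow the written instructions in the PureWick™ External Catheter instructions for use". The second item asks the same about the pictures, and the third asks whether the participant could place the catheter on themselves.

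On training, Section 7.1 says "Prior to the first void, each participant will be consented and trained on device instructions for use". Section 10.4, step 1.3, adds the video: "The participant will be trained on device use per the Instructions for Use and a training video". It continues: "The participant will be allowed to refer to any of the training materials that are available and provided to them throughout the study procedures".

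The questionnaire schedule at the end of Section 10.4 and the form itself both place the IFU Evaluation after the self-placement void. Protocol Section 11.4.2 plans an overall summary of the score. SAP Section 2.2.6, Table 16, shows it by device.

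**The concern.** The objective concerns a document: can people aged 12 to 21 understand the IFU? The measurement is taken when every respondent has already been taught the same content by other means. A participant who learned the steps from the training or the video can truthfully agree that the written instructions and pictures were understood, even if the document alone would have left them unsure.

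This matters because Section 4.2 says the study should inform use "in the outpatient or home setting where the external catheter is self-placed or placed by guardian/parent" and support potential labelling for an expanded population. Exclusion criteria 6 and 7 remove people with clinical training or home-care employment, which suggests that lay comprehension was of interest. A high score in Table 16 would naturally be read as evidence that the IFU works for adolescents, and the design does not supply that evidence.

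**Working it through.** The plan gives no figure to reproduce. Protocol Section 11.0 states that there is no hypothesis test, Section 6.2 sets no performance goal, and the IFU score has no pass mark. The check traces the order of events and asks what the score can identify.

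1. **Training comes first, for everyone.** Section 3.0 (device-use row), Section 7.1 and Section 10.4, step 1.3, all put training before the first void. Section 7.1 applies it to each participant. Only step 1.3 mentions the video.

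2. **Training materials remain available.** Step 1.3 lets participants consult any of them throughout, so the IFU is not the only source in use during self-placement.

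3. **Correction can follow.** For the self-placed void, step 2.3 has the HCP record whether the tubing connection was right and adjust it if not. Step 2.5 has the HCP ask for repositioning if placement is wrong.

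4. **The questionnaire comes last.** Appendix 7 is completed after the self-placed void, so after steps 1 to 3 above.

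5. **Sequence adds exposure for some.** Section 7.3.1 randomizes 1:1 to placement order. If allocation is even, 40 × 1/2 = 20 participants will have had an HCP placement before they self-place. Step 5.2 repeats Activities 1 to 4 for void 2, so as written step 1.3 also recurs for them.

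6. **Count.** Planned participants: 20 male + 20 female = 40 (Section 11.1). IFU ratings planned before training: 0. Share of ratings that reflect the IFU alone: 0/40 = 0%.

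7. **Identification.** Write the post-void score as the result of IFU + training + video + any correction. Training and video are given to all, so neither varies between participants and neither can be adjusted for. Sequence and HCP correction do vary, but Table 16 does not split by them. Splitting would in any case leave the training and video in every cell. More participants would narrow the spread of the estimate without changing what it estimates.

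8. **Direction and size.** Extra teaching on the same content would be expected to raise self-rated comprehension, so the likely bias favours the IFU. The documents hold no untrained rating, so no range can be computed.

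**The case against.** The best case for the plan has four parts. Training participants as young as 12 before they handle the device is reasonable. The objective does not say the IFU must be tested alone. Appendix 7 items 1 and 2 name the written instructions and the pictures, with free text for low scores. The HCP also records whether the connection and placement were correct, including whether a failed connection arose from not understanding how to make it (step 2.3; SAP Tables 5 to 7 and Listing 8). All of this is descriptive, with no threshold to pass.

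The first part stands, and the fix leaves training before placement. The others help less. Naming the source in a question does not remove what was learned elsewhere, the HCP records are also made after training, and a descriptive score must still describe what its label says.

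A reader might infer several stronger points that the documents do not support:

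- *That the labelling promises use without training.* The sentence "No special skills or additional training is required" is in the Urine Collection System guide (Appendix 3). The HCP sets up that system in this study (step 1.4), and Appendix 7 rates the catheter IFU. The catheter IFUs contain no such statement.
- *That the video is absent from ordinary home use.* The appendix text available does not mention one, but figures are missing and labelling copies are held separately (Section 5.1.1).
- *That someone at the site shows each participant how to do every step.* The protocol names no trainer and does not describe how the training is given.
- *That participant ease-of-use ratings are spoiled in the same way.* That objective carries no premise of untrained use.
- *That high scores would be due entirely to training.* The size of the effect cannot be known from this design.
- *That training should move to after Appendix 7.* Self-placed capture rate and wetness, both primary, would then be measured in untrained users. Participants would also self-remove the device untrained, where Section 8.2.1 and the catheter IFUs warn of skin injury. That is a substantive trade-off.

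**Conclusion.** The concern holds in a limited form. As designed, the IFU comprehension score measures comprehension after IFU, training and video, and for some participants after HCP correction as well. It cannot show whether the IFU itself is understood by ages 12 to 21. All 40 planned ratings are affected. The likely direction is favourable and the magnitude is unknown.

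This rests on two assumptions: that step 1.3 is carried out as written for every participant, and that the objective in Section 6.1 is meant to say something about the IFU as a document. If the sponsor intends only comprehension after training, the defect reduces to a label that promises more than the score delivers. The primary endpoints are not in question. This is a cheap improvement worth making before enrolment.

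**What to change.** Keep training before placement and change the order within step 1.3:

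- On the first pass through step 1.3, give the participant the printed catheter IFU and time to read it.
- Before the video and training, have the participant answer Appendix 7 items 1 and 2, reworded to ask about comprehension only. Remove the word *follow* from item 1, since it cannot be answered before an attempt.
- Continue with training, video, placement and HCP checks as planned.
- Repeat the existing Appendix 7 items after the self-placed void.
- In SAP Table 16, report the pre-training answers as the IFU comprehension score, with the post-void answers beside them. Add the matching column to Listing 15.

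If this is not done, label Table 16 as comprehension after IFU, training and video, and limit any conclusion on the IFU to that. Either way, Sections 3.0 and 7.1 should mention the video, as step 1.3 does.

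The cost is a few extra minutes per participant, two extra items (2 × 40 = 80 responses), an added block in one table and possibly lower scores. Device use and the primary endpoints are essentially unchanged. The pre-training answers remain self-ratings, so they show perceived comprehension and do not test it objectively.
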